5.3 Lifestyle Considerations

5.3.1 Meals and Dietary Restrictions

- 1 Participants should avoid eating a large meal for at least 1 hour prior to all scheduled supervised spirometry assessments.
- 2 Participants should refrain from consumption of grapefruit juice and St John's wort from the start of study intervention until the final dose. Study intervention can be taken with or without food.

5.3.2 Alcohol and Tobacco

1 Chronic alcohol or drug abuse within 2 years (at the investigator's discretion) is restricted prior to SV1 and throughout the conduct of the study.

Current tobacco smokers or prior tobacco smokers, with smoking history ≥ 10 pack-years (1 pack-year = 20 cigarettes smoked per day for 1 year) at SV1 are allowed. Never smokers are not allowed to enter the study. Any change in smoking status in the 12 weeks prior to enrolment or intention to change smoking status between enrolment and the end of follow-up will result in a screen failure. However, following change in smoking status, they will be eligible for rescreening. Smoking status changes during the study will be captured on the eCRF but the participant will be permitted to continue in the study.

5.4 Screen Failures

A screen failure occurs when a participant who has consented to participate in the clinical study is not subsequently assigned to study intervention. A minimal set of screen failure information is required to ensure transparent reporting of screen failure participants to meet the Consolidated Standards of Reporting Trials (CONSORT) publishing requirements and to respond to queries from regulatory authorities. Minimal information includes demography, screen failure details, eligibility criteria, and any SAE.

Individuals who do not meet the criteria for participation in this study (screen failure) may be rescreened, if one or more of the following occurs:

- There is reason to believe the reason for ineligibility was temporary (eg, exacerbation and/or background medication stability periods).
- Failure to achieve the required 70% compliance on any of the following: morning e-Diary, evening e-Diary, and PEF measurements during the 14 days preceding SV3.
- Any change in smoking status in 12 weeks prior to enrolment or intention to change smoking status between enrolment and end of follow-up will result in a screen failure. However, following a change in smoking status, participants will be eligible for rescreening.

Only one rescreening per participant is allowed in the study, when there is a reasonable expectation that the participant will become eligible for the study. Prior to rescreening, participants must be reconsented. Rescreened participants should be assigned the same participant number as for the initial screening.

Where an appropriate chest CT scan was performed within the last 6 months, such as for part of the previous screening process, this CT scan may be used for the study. This scan should be submitted at the time of screening, but can be repeated if the quality is not adequate for analysis.

If previously performed as part of the previous screening process, a second FSH test does not need to be performed. All other tests must be performed as per the SoA (Table 1).

5.5 Criteria for Temporarily Delaying Enrolment, Randomisation, or Administration of Study Intervention

6 STUDY INTERVENTION(S) AND CONCOMITANT THERAPY

Study interventions are all pre-specified, IMPs and NIMPs, medical devices and other interventions (eg, surgical and behavioural) intended to be administered to the study participants during the study conduct.

6.1 Study Intervention(s) Administered

Table 4 Study Interventions

Arm name	Mitiperstat (AZD4831)	Placebo
Intervention name	Mitiperstat (AZD4831)	Placebo
Type	Drug	Placebo
Dose formulation	Film-coated tablet	Film-coated tablet
Unit dose strength	5 mg	N/A
Dosage level	5 mg once daily Home administration by the participant should be in the morning. On days with an on-site visit, participant should be dosed at the site during the visit.	Once daily Home administration by the participant should be in the morning. On days with an on-site visit, participant should be dosed at the site during the visit.
Route of administration	Oral	Oral
Use	Experimental	Placebo-comparator
IMP or NIMP	IMP	IMP
Sourcing	Provided centrally by AstraZeneca	Provided centrally by AstraZeneca
Packaging and labelling	Study Intervention will be provided in bottles. Each bottle will be labelled in accordance with GMP and country regulatory requirements for labelling.	Study Intervention will be provided in bottles. Each bottle will be labelled in accordance with GMP and country regulatory requirements for labelling.
Current/former name(s) or alias(es)	N/A	N/A

GMP = Good manufacturing practice; IMP = Investigational Medicinal Product; N/A = not applicable; NIMP = Non-Investigational Medicinal Product

6.1.1 Medical Devices Including Combination Products with a Device Constituent

- 1) Medical devices (not manufactured by or for AstraZeneca) provided for use in this study are:
 - MIR Spirobank Smart spirometer (available in each study region)
 - MIR Spirobank II Smart (available in each study region) (SV1 screening visit only)
 - VitaloJAK® Cough Monitor (available in each study region where the cough substudy will be performed)
- 2) Instructions for medical device use are provided.
- 3) All medical device deficiencies (including malfunction, use error and inadequate labelling) shall be documented and reported by the investigator throughout the clinical investigation (see Section 8.4.13) and appropriately managed by AstraZeneca.

In addition to the medical devices described above, an e-Diary (a handheld device) will be used to complete the assessments described in Section 8.2.6. AstraZeneca's UNIFY application will be used on the handheld device for collection of e-Diary, PEF, and virtual spirometry data. The Medidata application for image handling is installed on the handheld device. A tablet installed with ZEPHYRx's application will display the data from the MIR Spirobank II Smart.

ArtiQ.QC will be integrated into ZEPHYRx application for an instant artificial intelligence-based over-reading of spirometry against ATS/ERS 2019 standards. Meanwhile ArtiQ.RBM software will also be utilised in ZEPHYRx and UNIFY, for risk-based quality management analysis of spirometry and identification of sites that may require quality improvement initiatives.

Both ArtiQ.QC and ArtiQ.RBM are not considered to meet the definition of a medical device as it only performs quality control and quality management functions. It will not be used as the basis for any clinical decision making or patient treatment.

The UNIFY application is not considered to meet the definition of a medical device as it performs only administrative study functions and collects and displays medical information. It does not process or analyse medical information for the purposes of treating or diagnosing participants.

The ZEPHYRx application is not considered to meet the definition of a medical device as it does not modify or alter the medical device data coming from the spirometer. The application will only be used for assessing if the participant meets the screening criteria for the study. It will not be used as the basis for any clinical decision making or patient treatment.

The Medidata application is not considered to meet the definition of a medical device as it only acts as a file transfer mechanism. The images captured in the application are not used for clinical decision making or patient treatment.

6.2 Preparation, Handling, Storage, and Accountability

- The investigator or designee (eg, pharmacist or study coordinator) must confirm appropriate conditions (eg, temperature) have been maintained during transit for all study intervention received at the site and throughout the entire study until authorisation is provided for on-site destruction or removal of the IMP, reflecting completion of the study. In the event of a temperature excursion detected at any time during the study, sites will follow the reporting procedures for notifying AstraZeneca (or designated party); release of IMP for clinical use can only occur once the event has been reviewed and approval is provided by AstraZeneca (or designated party).
- Only participants randomised in the study may receive study intervention, and only authorised site staff may supply or administer study intervention. All study intervention must be stored in a secure, environmentally controlled, and monitored (manual or automated) area in accordance with the labelled storage conditions with access limited to the investigator and authorised site staff.
- The investigator, institution, or the head of the medical institution (where applicable) is responsible for study intervention accountability, reconciliation, and record maintenance (ie, receipt, reconciliation, and final disposition records).
- Study medication will be dispensed to participants in bottles. Participants will be instructed to take one tablet per day in the morning.
- Further guidance and information for the final disposition of unused study interventions are provided in the pharmacy manual.

6.3 Assignment to Study Intervention

All participants will be centrally assigned to randomised study intervention, and have an E-code assigned, using an Interactive Response Technology/Randomisation and Trial Supply Management (IRT/RTSM) system. Before the study is initiated, the log in information and directions for the IRT/RTSM will be provided to each site.

Participants will be randomised 1:1 to mitiperstat (AZD4831) 5 mg or placebo at SV3 (Table 1). Randomisation will be stratified by country.

Study intervention will be dispensed at the study visits summarised in the SoA (Table 1).

Returned study intervention should not be re-dispensed to the participants.

The IRT/RTSM will provide to the investigator(s) or pharmacists the kit identification number

to be allocated to the participant at the dispensing visit.

Routines for this will be described in the IRT/RTSM user manual that will be provided to each centre.

6.4 Blinding

The study will be blinded to both participants and investigators/site staff as well as to AstraZeneca staff. With the formation of the URC and DRC (see Appendix A 5) the study will become unblinded to the AstraZeneca staff assigned to these committees (including those with clinical, medical, statistical, and programming expertise) who will form a firewalled URC for administrative purposes and will all be independent from the study team (see Appendix A 5). The URC will be responsible for conducting the administrative IA whereas the DRC will be responsible for safety monitoring.

The randomisation list should be sent to the personnel analysing the PK samples. Pharmacokinetic samples will be analysed by the bioanalytical laboratory performing the bioanalyses only for participants on active treatment, as referenced in Section 8.5.2. To allow for the appropriate selection of samples, the bioanalytical laboratory will, therefore, have access to the treatment codes but will not share the codes with AstraZeneca or others involved in the study until the blinding is broken for the study.

The randomisation code should not be broken except in medical emergencies when the appropriate management of the participant requires knowledge of the treatment randomisation. The investigator documents and reports the action to AstraZeneca, without revealing the treatment given to the participant to the AstraZeneca staff.

AstraZeneca retains the right to break the code for SAEs that are unexpected and are suspected to be causally related to an investigational product and that potentially require expedited reporting to regulatory authorities. Randomisation codes will not be broken for the planned analyses of data until all decisions on the evaluability of the data from each individual participant have been made and documented.

The IRT/RTSM will be programmed with blind-breaking instructions. In case of an emergency, in which the knowledge of the specific blinded study intervention will affect the immediate management of the participant's condition (eg, antidote available), the investigator has the sole responsibility for determining if unblinding of a participant's intervention assignment is warranted. Participant safety must always be the first consideration in making such a determination. If a participant's intervention assignment is unblinded, AstraZeneca must be notified within 24 hours after breaking the blind.

6.5 Study Intervention Compliance

The first dose of study intervention will be administered in clinic on the day of randomisation. Participants will receive study intervention at the site on visit days and at home between visits.

When participants are dosed at the site, they will receive study intervention directly from the investigator or designee, under medical supervision. The date and time of dose administered in the clinic will be recorded in the source documents and recorded in the eCRF. The dose of study intervention and study participant identification will be confirmed at the time of dosing by a member of the study site staff other than the person administering the study intervention.

When participants self-administer study intervention(s) at home, compliance with study intervention will be assessed at each visit. Compliance will be assessed by counting returned tablets during the site visits and comparison of this data to e-Diary self-administration data, and/or direct questioning can be used to confirm details. Compliance will be documented in the source documents and eCRF. Deviation(s) from the prescribed dosage regimen should be recorded in the eCRF.

A record of the number of the mitiperstat (AZD4831)/placebo tablets dispensed to and taken by each participant must be maintained and reconciled with study intervention and compliance records. Intervention start and stop dates, including dates for intervention delays will also be recorded in the eCRF.

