8.2.6 E-Diary

The e-Diary will be provided to participants at Visit SV2, at which point they will receive

training on its use.

Participants will record information in their e-Diary twice a day.

The participant will be asked to bring the e-Diary on with them to all on-site visits.

The following parameters will be reported by participants according to the SoA (Table 1):

- COPDCompEx parameters
- BCSS
- OCS use, antibiotic use, and hospitalisation
- Cough VAS
- Study intervention administration at home
- EXACT
- CAT
- Self-photos of skin affected with rash/skin reaction

Participants must demonstrate a compliance of at least 70% during the 14 days preceding SV3 to be eligible for randomisation (defined as completing the daily diary for any 10 mornings, any 10 evenings, and performing PEF for any 10 morning and any 10 evenings).

During the study treatment period, daily eDiary compliance is critical for overall symptom rating, reliever medication use, and change in PEF. The investigator/authorised delegate should check the participant's adherence to the daily eDiary at each visit during the study and at any time during the study. If it drops below 80% to 85%, sites should take steps to ask the participant about the reason and to encourage the participant to regularly complete the eDiary.

See Appendix I for the BCSS and Cough VAS assessments to be completed.

If technical or other issues prohibit completion, an appropriate back-up option may be considered with prior approval from AstraZeneca.

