4.1.10 Study Drug Compliance

4.1.10.1 Definitions and Derivations

Compliance with investigational product (IP) will be calculated using the following equation:

IP Compliance (%) =
$$\frac{Number\ of\ doses\ taken}{Number\ of\ intended\ doses} \times 100$$

The number of intended doses is equal to one tablet per day throughout the duration of the study for each patient, and thus it is approximated by treatment start date minus treatment end date +1, i.e. independent of any dose interruptions.

The number of doses taken is the "actual exposure" from section 4.7.1.1, i.e. the difference between dispensed and returned tablets as recorded in eCRF. If any 'Amount Returned' field in the Drug Accountability CRF page is blank, then the Number of Doses taken – and therefore IP Compliance – is not calculated.

Participants' IP compliance will be categorized in <80%, from 80% (included) to 120% (included), >120%. Participants having IP compliance between 80% to 120% inclusive will be defined as treatment compliant.

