4.7.1 Exposure

4.7.1.1 Definitions and Derivations

Exposure duration is calculated only for participants in the Safety population as the total number of days on study drug and is calculated as:

Exposure duration (days) = Last drug application date -First drug application date + 1 - (treatment interruption period)

The date from end of treatment phase is to be used for last drug application date.

Exposure as measured by amount tablets administered calculated as:

 $Actual\ exposure\ (tablets) = tablets\ dispensed-tablets\ returned$

Note that if any 'Amount Returned' field in the Drug Accountability CRF page is blank, then this formula will not be calculated.

If any of the first or last dates are missing or partially missing, then imputed dates will not be used, and study drug exposure is set to missing.

Total amounts of doses received will be calculated as number of days where at least one dose amount of >0 is administered. The first dose of the intervention period intended to be the SV3 dose and the intended last dose of the intervention period is SV7 dose.

Total time of exposure (patients-years) is calculated as:

Total time of exposure (patients – years) =
$$\frac{1}{365.25} \times \sum_{Patient} Exposure duration$$

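### One blank tablet-return field voids a participant's compliance and tablet exposure, although home dosing is also recorded in the e-Diary

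*Protocol*

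**What the plan says.** **Protocol.** Section 6.5 states: "Compliance will be assessed by counting returned tablets during the site visits and comparison of this data to e-Diary self-administration data", and adds "and/or direct questioning can be used to confirm details". It also has the date and time of clinic doses entered in the eCRF. Section 8.2.6 lists "Study intervention administration at home" among the e-Diary items and says "Participants will record information in their e-Diary twice a day".

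**SAP, compliance (4.1.10.1).** Doses taken are "the difference between dispensed and returned tablets as recorded in eCRF". One empty return count is enough to stop the derivation: where such a "field in the Drug Accountability CRF page is blank, then the Number of Doses taken" is left underived, and the compliance percentage with it. Intended doses are written as treatment start date minus treatment end date, plus one.

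**SAP, exposure (4.7.1.1).** Actual exposure in tablets carries the same rule: if any Amount Returned "field in the Drug Accountability CRF page is blank, then this formula will not be calculated". A second dose measure has no such rule: "Total amounts of doses received will be calculated as number of days where at least one dose amount of >0 is administered". Exposure duration has none either.

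The SAP does not use e-Diary dosing for either quantity. It specifies no fallback and no row for participants whose compliance cannot be calculated. SAP Section 2, which lists changes from the protocol, does not mention leaving the diary out. The amendment history has an October 2024 entry for an updated compliance calculation, giving data issues as the reason and no detail.

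**The concern.** The trial collects two records of dosing. The SAP keeps one and makes it all-or-nothing, so valid counts from other bottles are thrown away even when the diary is complete.

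The loss could also be selective. The Schedule of Activities places the return of all study supplies at SV7 or the early discontinuation visit. Protocol 7.2 asks for that visit on withdrawal only if possible, and participants lost to follow-up have by definition stopped attending. Appendix B 4 foresees that some participants will not return medication. The last bottle is therefore the one most easily left uncounted. Diary entries do not depend on that visit.

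The trial tests a single dose, expected to give roughly 56% MPO inhibition (Protocol 4.3). After a null result, a reader will ask whether the drug was taken. The Per Protocol Set has been dropped (SAP Section 2), so Table 14.1.18 is the only planned summary of percentage compliance.

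**Working it through.** The plan states no figure for blank returns, so there is nothing to reproduce. The check has four steps.

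**1. What one blank discards.** Drug is dispensed at SV3, SV4 and SV5 (Days 1, 28 and 84), and treatment runs to Day 168. Assume one return field per dispensing; the CRF page itself is not in the documents. For a participant completing 24 weeks:
- First bottle blank: counts covering about 168 − 28 = 140 of 168 days (83%) are discarded.
- Last bottle blank: counts covering about 84 of 168 days (50%) are discarded.

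**2. How many participants could lose their value.** With k fields and an assumed, independent blank probability q per field, P(not calculated) = 1 − (1 − q)^k. Take k = 3 for three dispensings and k = 2 when SV5 and SV7 are combined. Counts are out of 406.

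| q (assumed) | k = 2 | k = 3 |
|---|---|---|
| 1% | 2.0% (8) | 3.0% (12) |
| 2% | 4.0% (16) | 5.9% (24) |
| 5% | 9.8% (40) | 14.3% (58) |
| 10% | 19.0% (77) | 27.1% (110) |

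**3. Effect on the summaries.** Assume three fields and, for the shares, a true 20% of participants below 80% compliance and none above 120%.

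- *Share among those with a value.* If blanks are unrelated to adherence (5% per field in both groups), the share stays at 20%. If they are related (3% per field in adherent participants; 10%, 20% or 30% in the others), the share is 0.2(1 − q)³ / [0.2(1 − q)³ + 0.8 × 0.97³], which gives 16.6%, 12.3% or 8.6%.
- *Share of the full analysis set.* SAP 3.4 takes percentages out of the population total unless stated otherwise. With 5% random blanks, 0.95³ = 0.857. The table would show 20% × 0.857 = 17.1% below 80% and 80% × 0.857 = 68.6% compliant. Both are too low, and 14.3% is left unaccounted for.
- *Mean.* Suppose 14% have no value, with true means of 70% in them and 95% in the rest. The table reports 95%, against 0.86 × 95% + 0.14 × 70% = 91.5%. Both lie inside the SAP's 80% to 120% compliant band.

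**4. The intended-doses formula.** For treatment from Day 1 to Day 168, the formula as written gives 1 − 168 + 1 = −166. End minus start plus one gives 168.

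**The case against.** The best defence is that the rule is cautious and little depends on it. Treating a blank as nothing returned would count every dispensed tablet as taken and overstate compliance. Compliance is descriptive, and primary censoring uses last-dose, last-diary and intercurrent-event dates. Week 12 plasma concentrations and sputum MPO also bear on whether drug was taken. Diary dosing may be incomplete in the same people. All of this stands and limits the point to a minor one. It does not justify discarding the valid counts. The plasma evidence has gaps too: it normally comes from active-arm samples only, and the SAP schedules it at Day 1 and Week 12.

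Several stronger readings are tempting, and the documents do not support them:
- *The SAP contradicts the protocol.* Protocol 6.5 describes how sites assess compliance. It prescribes no analysis formula, so the SAP omits an available source.
- *The non-adherent are the ones removed.* This is plausible but not shown. A blank may equally be a site recording gap.
- *Affected participants leave the exposure tables.* Only the tablet count is lost. Duration and total doses received remain in Tables 14.3.1.1 and 14.3.1.2.
- *The compliant percentage is inflated.* With the default denominator in SAP 3.4 it is lowered.
- *Early stoppers are non-compliant.* Intended doses run only to treatment end, so someone who stops on Day 10 having taken every tablet is 100% compliant.
- *Rash makes the loss differ by arm.* Participants stopping for rash are asked to attend a discontinuation visit, where supplies are returned. Nothing links rash to blank returns.

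**Conclusion.** The point holds as a minor one. The SAP discards usable tablet counts whenever one return field is blank, and it ignores a dosing record that the protocol names as the comparison source. Mean compliance may therefore describe a selected subset.

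The size and direction of any bias cannot be determined from the documents. The 2% to 27% range rests entirely on assumed blank rates, and the shifts in step 3 on assumed differences between participants with and without a value. If blanks are unrelated to adherence, the mean and the shares among calculable participants are unbiased. What remains is lost information and category percentages that do not add up.

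The primary analysis, exposure duration and total doses received do not change. The reversed dates are a plain drafting error.

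**What to change.** In SAP 4.1.10.1 and 4.7.1.1:
- When a return count is blank, take the doses for that dispensing interval from the daily dosing records: e-Diary home doses plus clinic doses in the eCRF.
- Set compliance and tablet exposure to missing only if both sources are missing for an interval.
- Report by arm the number derived this way and the number still not calculable.
- Show e-Diary compliance beside the tablet-count figure as a supportive summary.
- Write intended doses as treatment end date minus treatment start date, plus one.

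The cost is SAP wording and some programming on data already collected. The downside is that the diary may under-record doses, so a filled interval could look less compliant than it was. Showing both figures makes that visible.
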